## 8.7. Analysis of Time to Rescue Medication

Time to rescue medication quantiles:

```
proc lifetest data=...;  
  time aval*cnsr(1);  
  strata trtp;  
run;
```

The input dataset needs to have a record per subject per treatment (ZNS or Placebo).

Explanation of variables:

1. TRTP: planned treatment at the time of assessment
2. AVAL: time to rescue medication (censored at 24 hours of subject does not take any rescue medication)
3. CNSR: censoring indicator (1 – time is censored, 0 – time is not censored)

Cox proportional hazards model:

```
proc phreg data=...;  
  class trtp aperiod weightcat base;  
  model aval*cnsr(1) = trtp aperiod weightcat base;  
run;
```

Explanation of variables:

1. TRTP: planned treatment at the time of assessment
2. AVAL: time to rescue medication (censored at 24 hours of subject does not take any rescue medication)
3. CNSR: censoring indicator (1 – time is censored, 0 – time is not censored)
4. APERIOD: treatment period number (1 or 2)
5. WEIGHTCAT: weight category (<50 kg or >=50 kg)
6. BASE: pre-dose headache severity

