#### **5.2.1.6. Repeated Measures Analysis**

The primary endpoint will also be analyzed using a generalized estimating equation (GEE) using results from all post-dose timepoints (0.5, 1, 2 and 24 hours). The model will include treatment, period, sequence, weight group (at randomization), predose (immediately prior to study drug administration) headache pain intensity, timepoint as time factor and treatment by timepoint interaction. The logit link function will be used with an unstructured within subject covariance matrix. Odds ratio, p-value for the treatment effect and the corresponding 95% confidence interval will be presented for each timepoint. If the model fails to converge due to the unstructured covariance matrix, a simpler covariance matrix will be employed in the order of 1) autoregressive (1) [SAS PROC GEE type = AR(1)], 2) exchangeable [type = EXCH]. The first covariance structure that does not have a convergence problem will be the one used for the analysis.

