- Time to rescue medication. For those subjects who did not use rescue medication, the time to rescue medication is censored at 24 hours after dosing. Additionally, descriptive summary of time to rescue medication will be presented for those subjects who did take a rescue medication. Note: if subject diary includes records of rescue medication that started prior to the start of migraine, such medications will be ignored as incorrect diary entry. If rescue medications are recorded with missing start date/time, time to rescue medication will be imputed as zero.

For all proportion endpoints, a GEE model similar to the primary analysis will be conducted for the low dose group and high dose group separately.

For the time to use of rescue medication, a Cox proportional hazards model for crossover data ([France et al 1991](#)) with treatment, period, weight, and baseline headache pain intensity will be used.

Time to use of rescue medication will also be presented graphically using the Kaplan-Meier estimates.

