## 8. CODE SAMPLES

### 8.1. Primary analysis GEE model

```
proc genmod data=...;
  class trtp aperiod trtseqp usubjid weightcat base;
  model avalc(event='Y') = trtp aperiod trtseqp weightcat base / dist=binomial
link=logit type3;
  repeated subject=usubjid(trtseqp) / type=UN within=aperiod;
  lsmeans trtp / diff cl oddsratio ilink;
run;
```

The input dataset needs to include a record per each subject/treatment period. Explanation of variables:

1. TRTP: planned treatment at the time of assessment
2. APERIOD: treatment period number (1 or 2)
3. TRTSEQP: planned sequence of treatments (ZNS-Placebo or Placebo-ZNS)
4. USUBJID: unique subject identifier
5. WEIGHTCAT: weight category (<50 kg or >=50 kg)
6. BASE: pre-dose headache severity
7. AVALC: response variable (Y = response achieved, N = not achieved).

Odds ratios, their confidence intervals and p-values will be found in the Diff's ODS dataset.

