## 8.5. Sensitivity Analysis Repeated Measures Model

```
proc genmod data=...;
  class trtp aperiod trtseqp usubjid weightcat base atptn;
  model avalc(event='Y') = trtp aperiod atptn trtp*atptn weightcat base/
  dist=binomial link=logit type3;
  repeated subject=usubjid(trtseqp) / type=UN within=aperiod*atptn;
  lsmeans trtp*atptn / diff cl oddsratio ilink;
run;
```

The input dataset needs to include a record per subject, period (1 or 2) and timepoint (0.5 hr, 1 hr, 2 hr or 24 hr post-dose).

The variables are the same as in the primary analysis GEE model, plus:

- ATPTN: timepoint number (0.5 hr, 1 hr, 2 hr or 24 hr post-dose).

In case of convergence problems type=AR(1) and type=EXCH will be tried.

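### The sample Cox code for time to rescue medication treats a child's two attacks as independent, although section 5.3 specifies a crossover model; the treatment interval is likely too wide (minor: sequence is missing from the repeated-measures code)

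*SAP*

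**What the plan says.** **Time to rescue medication.** SAP section 5.3 calls for "a Cox proportional hazards model for crossover data" with treatment, period, weight and baseline pain intensity. Times are censored at 24 hours after dosing when no rescue medication is used. Section 8.7 describes the data as follows: "The input dataset needs to have a record per subject per treatment (ZNS or Placebo". That sentence stands above the PROC LIFETEST step, but the Cox step names no other dataset and has period as a covariate, so it too needs a record per period. The Cox step consists of "class trtp aperiod weightcat base" and "model aval*cnsr(1) = trtp aperiod weightcat base", and nothing else.

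**Primary model, for comparison.** Section 8.1 clusters on the child: "repeated subject=usubjid(trtseqp) / type=UN within=aperiod".

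**Repeated-measures model.** Section 5.2.1.6 states: "The model will include treatment, period, sequence, weight group (at randomization", among other terms. The code in section 8.5 reads "model avalc(event='Y') = trtp aperiod atptn trtp*atptn weightcat base". It names `trtseqp` in the CLASS statement and in the subject nesting, but not among the model terms.

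**The concern.** The covariates in the Cox code match the text. The missing piece is the pairing. Without a subject identifier, PROC PHREG computes its standard errors as if 240 children with two attacks each were 480 unrelated records. Treatment is compared within the child, so positive correlation between a child's two attacks makes the true sampling variance smaller than the one the code reports. The confidence interval and p-value for this secondary endpoint then lack their nominal properties, and the precision that a crossover is meant to buy is not credited.

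Text and code also conflict. A programmer working from 5.3 and one working from 8.7 could report different intervals, and a choice made after unblinding would be post hoc. The sequence omission in 8.5 is a text-code conflict of the same kind, with far less at stake.

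**Working it through.** **1. Text against code.** No stated figure is involved, so the first check is term by term.

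| Item | Text | Code |
|---|---|---|
| Cox covariates | treatment, period, weight, baseline pain (5.3) | the same four (8.7) |
| Cox pairing | crossover model (5.3) | none: no STRATA, ID, COVS(AGGREGATE) or RANDOM (8.7) |
| Subject identifier | – | in the variable lists of 8.1 and 8.6, absent from 8.7 |
| Repeated-measures sequence term | listed (5.2.1.6) | absent from MODEL (8.5), present in the primary MODEL (8.1) |

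**2. Direction of the error.** For a within-child contrast with correlation ρ between the two records (on the scale of the score contributions), the true variance is roughly (1 − ρ) times the variance under independence. The code's SE is therefore too large by about 1/√(1 − ρ). An excess of 15% corresponds to ρ = 1 − 1/1.15² = 0.24, and an excess of 45% to ρ = 1 − 1/1.45² = 0.52. At ρ = 0 there is no excess.

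**3. Simulation with a normal child effect.** From the SAP: 240 high-dose children (1.2), two periods, 1:1 sequences (2.3), rescue from 2 hours (1.1), censoring at 24 hours (5.3). Assumed: hazard 0.03 per hour and the variance of the child effect on the log hazard. There were 300 null runs and 200 runs at log HR −0.4 per setting. Robust means a covariance clustered by child.

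| Child variance | Code SE | Robust SE | True SD | Code SE / true SD | Null rejection, code vs robust | Power, code vs robust |
|---|---|---|---|---|---|---|
| 0 | 0.126 | 0.126 | 0.130 | 0.97 | 5.0% vs 6.0% | 85.0% vs 84.0% |
| 1 | 0.125 | 0.103 | 0.098 | 1.28 | 2.0% vs 4.7% | 71.5% vs 79.5% |
| 2 | 0.124 | 0.091 | 0.089 | 1.39 | 0.7% vs 5.3% | 52.5% vs 72.5% |
| 4 | 0.125 | 0.079 | 0.081 | 1.54 | 0.0% vs 6.3% | 29.5% vs 70.5% |

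With 300 runs, the Monte Carlo SE of a 5% rejection rate is √(0.05 × 0.95/300) = 1.3 points, so the robust column is compatible with 5% throughout. At variance 1, the null half-width on the log scale is 1.96 × 0.125 = 0.245 with the code and 1.96 × 0.103 = 0.202 with the robust SE.

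Weight group is constant within a child, so its error runs the other way. For variances 1 to 4 the code's SE is about 0.145 against a true SD of 0.166 to 0.180, with null rejection of 9 to 11%.

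**4. Simulation with gamma frailty.** Again 240 pairs, rescue from 2 hours and censoring at 24 hours, with assumed frailty variance rising from 0.25 to 2 over four settings. The code's SE is 0.104 to 0.126 against a true null SD of 0.087 to 0.092. The outer bounds of the ratio are 0.104/0.092 = 1.13 and 0.126/0.087 = 1.45, an excess of roughly 15 to 45%. Null rejection with the code is 0.2 to 1.8%. Power at HR 0.75, from the lowest to the highest variance:

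| Analysis | Power |
|---|---|
| Code as written | 64 / 57 / 38 / 16% |
| Cluster-robust | 71 / 68 / 59 / 49% |
| Stratified by subject | 55 / 54 / 48 / 44% |

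**5. Sequence term.** With 1:1 sequences and period already in the model, adding sequence moved a simulated 2-hour log odds ratio by 0.001 on average (SE 0.16), and by 0.01 with 20% dropout in period 2.

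**The case against.** The best defence is that little depends on this. Time to rescue is the last-listed secondary endpoint, and the repeated-measures GEE is supportive. The tests carry no multiplicity adjustment (section 2), so no later test hangs on this p-value. The primary code clusters on the child and includes sequence. The size of the distortion rests on a correlation and an event rate that the SAP does not give. All of this stands, and it limits the severity. It does not remove the conflict between 5.3 and 8.7.

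It could also be said that sample code is shorthand. That is weak here: 8.1 spells out the subject clustering and lists the identifier, while 8.7 does neither.

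Four stronger readings are tempting and not supported:

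- **The hazard ratio is wrongly pulled toward 1.** A reader might infer this because the code's average log HR falls short of the simulated child-level value (−0.316 against −0.4 at variance 1 in step 3). That gap is the difference between a marginal and a child-conditional hazard ratio. The SAP does not say which it targets, and a robust SE leaves the point estimate unchanged.
- **False-positive treatment claims.** With positive correlation the treatment test is conservative.
- **Stratifying by subject is the natural repair.** It has less power than the robust analysis in all four settings of step 4, and less than the existing code at the lowest variance (55% against 64%). It cannot estimate weight, which 5.3 lists. It also drops children treated in one period only, whom section 2.1.2 keeps in the FAS.
- **The missing sequence term makes the repeated-measures result unfit to support the primary one.** That model differs from the primary by design (four time points, an interaction), and step 5 suggests a negligible shift.

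**Conclusion.** Wrong as written, and it should be fixed, but it does not threaten the trial's main conclusion. The code in 8.7 is not the crossover model that 5.3 specifies. For an assumed frailty variance of 0.25 to 2, the treatment SE is about 15 to 45% too large, null rejection is 0.2 to 1.8%, and power at HR 0.75 falls short of the cluster-robust analysis by 7 points (71 − 64) to 33 points (49 − 16). These sizes are illustrative. They depend on the assumed within-child correlation and hazard, and they vanish when the correlation is zero. The direction, an interval that is too wide for treatment, needs only that a child's two attacks be positively correlated.

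The conflict between 5.2.1.6 and 8.5 is real but clerical, and its expected effect on the estimate is small. The primary analysis is untouched by either point.

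**What to change.** - **Section 8.7:** change the call to `proc phreg covs(aggregate)` and add `id usubjid;`, with USUBJID in the variable list. All four covariates of 5.3 and all FAS children stay in.
- **Section 5.3:** add one sentence saying that the standard error of the Cox model is clustered by subject, and confirm that this agrees with the crossover reference cited there (its content was not used here). If a subject-stratified model is also wanted, label it supportive and note that it targets a child-conditional hazard ratio, omits weight and uses only children treated in both periods.
- **Section 8.5:** add `trtseqp` to the MODEL statement so that it matches 5.2.1.6.

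The cost is a few words of code in two places and one sentence of text. No new data are needed and the primary analysis does not change. The edit should be made before Part 1 is unblinded.

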Eligible placebo non-responders will be randomized to one of two treatment sequences within their respective body weight stratum determined immediately prior to randomization: ZNS followed by placebo or placebo followed by ZNS ([Table 1](#)). Subjects weighing less than 50 kg will be allocated randomly to receive ZNS 2.5 mg or 1 mg in a 5:1 fashion during the ZNS treatment. Subjects weighing at least 50 kg will be allocated randomly to receive ZNS 5 mg or 2.5 mg in a 5:1 fashion during the ZNS treatment ([Table 2](#)). Following randomization, subjects will have up to 6 weeks to treat a migraine attack of moderate or severe intensity. During each treatment period, subjects will treat a single moderate to severe migraine attack with study drug within approximately 20 minutes of the headache pain reaching moderate or severe intensity. Headaches occurring while the child is at school will not be treated with study drug. Headache pain intensity will be assessed by the subjects immediately prior to treatment with study drug and at 30 minutes, 1, 2, and 24 hours postdose using a subject diary containing the 4-point headache pain intensity scale. Associated migraine symptoms will also be assessed at these time points. Subjects who do not obtain satisfactory relief of migraine pain by 2 hours after taking study drug will be permitted to treat with their protocol-allowed pre-study acute migraine medication (eg,

nonsteroidal anti-inflammatory drugs [NSAIDs] or acetaminophen) at that time or at any time thereafter, if the headache does not resolve or if it recurs, with the exception that all triptans and ergot derivatives are prohibited for 24 hours following the dose of study treatment. After treating a migraine attack in the first treatment period, the subject will return to the study site to receive study drug for the second treatment period. Subjects will then have up to 6 weeks to treat a second migraine attack of moderate or severe intensity.

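### The Cox sample code for time to rescue (SAP 8.7) names no tie method, so Breslow applies by default; if many rescues share one recorded time, the hazard ratio can be pulled toward 1 and the test made conservative

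*SAP*

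**What the plan says.** Section 5.3 lists time to rescue medication among the secondary endpoints of Part 1. Times are censored at 24 hours, and the analysis is "a Cox proportional hazards model for crossover data" with treatment, period, weight and baseline pain intensity. If the start of a rescue medication was not recorded, "time to rescue medication will be imputed as zero".

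Section 8.7 gives the code. On data layout it says: "The input dataset needs to have a record per subject per treatment (ZNS or Placebo"). The Cox step is a PROC PHREG call with the statement "model aval*cnsr(1) = trtp aperiod weightcat base". It has no TIES= option, no STRATA or ID statement and no frailty term. No section of the SAP names a tie method.

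On when rescue may be taken, section 1.1 says: "Subjects who do not obtain satisfactory relief of migraine pain by 2 hours after taking study drug will be permitted to treat", and it continues that this may be "at that time or at any time thereafter, if the headache does not resolve or if it recurs". Section 2 sets every test at a two-sided 5% level.

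**The concern.** With no TIES= option, PHREG uses Breslow's approximation. That is general software knowledge; the SAP does not state it. Breslow is accurate when few events share a time value. When many do, it moves the hazard ratio toward 1 and overstates the standard error, so the test rejects less often than its stated 5%.

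Two features of the plan make shared values plausible. Every attack becomes eligible for rescue at the same elapsed time, which is also when the 2-hour diary rating falls due. And every rescue with an unrecorded start is placed at exactly zero. At stake are the estimate and the power for the only time-to-event efficacy endpoint. A further risk is that the tie method is chosen after unblinding.

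**Working it through.** **Is there a figure to reproduce?** No. The SAP gives no hazard ratio, event count, tie share or power for this endpoint. Its inputs are 240 high-dose children (section 1.2), one record per child per treatment, the 24-hour limit and the 5% level. Everything else below is an assumption.

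**1. Limiting case: every event at one time, unpaired.** The Breslow hazard ratio then equals the risk ratio p1/p0, with variance 1/d1 + 1/d0. The correct variance of the log risk ratio is 1/d1 − 1/n1 + 1/d0 − 1/n0. Assume a true hazard ratio of 0.65.

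- Placebo risk 40%: p1 = 1 − 0.60^0.65 = 0.2825, so Breslow gives 0.2825/0.40 = 0.706. Events are 240 × 0.2825 = 67.8 and 96. The Breslow variance is 1/67.8 + 1/96 = 0.0252, against 0.0252 − 2/240 = 0.0168. Power is 59% against 76%.
- Placebo risk 60%: p1 = 1 − 0.40^0.65 = 0.449, so Breslow gives 0.748. Power is 62.5% against 90.5%.

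This fixes the direction and the upper end.

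**2. Pairs within a child (model stratified by child).** Let b be the log hazard ratio. Let nA be the pairs in which the ZNS attack is rescued first, nB those in which the placebo attack is, and nT the pairs rescued at the same recorded time.

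- A tied pair contributes e^b/(1+e^b)² under Breslow. Under Efron it contributes twice that, a constant factor that changes nothing. Under EXACT it contributes 1, that is, no information.
- The default (or Efron) estimate is therefore (nA + nT)/(nB + nT). The EXACT estimate is nA/nB.
- At b = 0 the score is (nA − nB)/2, with true variance (nA + nB)/4, but the default information is (nA + nB + 2nT)/4. The squared test statistic is deflated by (nA + nB)/(nA + nB + 2nT), so the test is conservative whenever nT > 0.

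**3. Size under assumed tie shares.** Simulated: 240 attacks per treatment, true hazard ratio 0.70, a point mass at 2 hours, 25% later rescue up to 24 hours, treatment term only. The stratified case adds a child frailty with variance 0.5. Two stratified sets were run.

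| Placebo attacks rescued at exactly 2 h | Unpaired HR, Breslow v Efron | Unpaired power | Stratified power, default v EXACT (set 1; set 2) |
|---|---|---|---|
| 10% | negligible difference | no difference | set 2: 48% v 50% |
| 20% | 0.71 v 0.70 | 59% v 62% | 47% v 52%; 53% v 58% |
| 30% | 0.72 v 0.70 | 64% v 71% | 49% v 60%; 56% v 67% |
| 40% | 0.74 v 0.70 | 65% v 77% | 47% v 67%; 57% v 74% |

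A second unpaired run at 40% gave 0.74 v 0.71 and 61% v 73%. Absolute power differs between sets because it depends on assumptions that the SAP does not supply; the gaps are the result. Across variations of these assumptions the loss is about 3 points unpaired and 5 to 8 stratified at a 20% share. At 40% it is about 11 to 12 unpaired and 17 or more stratified.

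Type I error at 40%: unpaired 1.9% (Breslow) v 4.3% (Efron); stratified 1.1 to 1.3% (default) v 4.9 to 5.1% (EXACT). Stratified at 20%: 3.1% v 4.4 to 4.6%.

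**4. The same question by share of the rescue hazard at 2 hours** (unpaired, true hazard ratio 0.65, placebo risk 40% or 60%).

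| Share at 2 h | HR, Breslow | HR, Efron | Power gained with Efron |
|---|---|---|---|
| 25% | 0.651–0.658 | 0.646–0.649 | 0.5–2 points |
| 50% | 0.670–0.678 | 0.650–0.654 | 4–5 points |
| 80% | 0.676–0.723 | 0.640–0.663 | 11–13 points |
| 100% | 0.703–0.749 | 0.651–0.665 | 15–26 points |

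With no mass at 2 hours and times recorded on a 15-minute grid, the power difference is under 1 point. Ordinary rounding of times is not the issue.

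**5. What the tie option does not touch.** With no ties and a within-child correlation of 0.4, the printed code rejects a true null 1.6% of the time under either tie method, because it treats the two records as independent.

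**The case against.** A reader might infer that the plan produces heavy ties, so that the hazard ratio will be biased and a real benefit on rescue use missed. The SAP does not support that. A common time of eligibility is not a common time of event: section 1.1 allows rescue at 2 hours or at any later time, section 2.5.1.1 foresees rescue before 2 hours, and section 5.3 counts rescue by 2, 3, 4 and 24 hours. Rescue is handled by start date and time, so a tie needs identical recorded elapsed times. The number of times set to zero is unknown and was not simulated. The larger effects need much of the rescue on one value: at 20% and 40% of placebo attacks with a further 25% later, that is 20/45 = 44% and 40/65 = 62% of rescue events. All of this stands, and it makes the point conditional.

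It also stands that rescue use is tested separately by GEE at four cut-offs, which tie handling does not affect; that the error, where present, is conservative; and that section 8 offers sample code.

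A further objection is that stratification by child is not settled by the visible text. Section 5.3 lists weight as a covariate, and weight group at randomization is constant within a child, so it would drop out of a child-stratified model. That is right, and it is why the remedy has two branches.

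What does not stand is that the matter vanishes once the pairing is corrected. Stratifying removes ties between children, but a child rescued at the same recorded time in both attacks still counts toward a hazard ratio of 1 under both Breslow and Efron.

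**Conclusion.** The gap is real and its direction is certain; its size is not known. Section 8.7 leaves tie handling to a default that can shrink the hazard ratio and make the test conservative, in a setting where tied times are plausible. By assumed share of placebo attacks rescued at exactly 2 hours, the consequence is negligible near 10%, small at 20% and material at 40%. These figures rest on an assumed point mass at 2 hours, assumed hazard ratios of 0.65 to 0.70, an assumed later-rescue rate and frailty, and models with the treatment term only.

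This is a low-priority specification point on one of many secondary endpoints. The larger fault in the same code is that a child's two records are treated as independent although section 5.3 names a crossover model. A reader should not take a TIES= option as curing that.

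**What to change.** When section 8.7 is reconciled with the crossover Cox model named in section 5.3, add the tie method to the MODEL statement and one sentence to section 5.3:

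- if the model is stratified by child, TIES=EXACT (Efron does not help for pairs tied within a child);
- if an unstratified model with child-clustered robust variance is used, TIES=EFRON.

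The cost is one option and one sentence, written before unblinding. One caution: with a true point mass at 2 hours, the EXACT stratified hazard ratio can lie further from 1 than the truth (0.65 against a true 0.70 at a 40% share, where the default gives 0.75). The gain in that branch is correct test size and power, not an unbiased hazard ratio.
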